MDS-UPDRS	Movement Disorders Society-Unified Parkinson's Disease Rating Scale
MedDRA	Medical Dictionary for Regulatory Activities
MMSE	Mini-Mental State Examination
OC	observed cases
PCI	potentially clinically important
PD	Pharmacodynamic(s)
PD NMS	Parkinson's disease non-motor symptoms
PDP	Parkinson's disease psychosis
PGI-I	Patient Global Impression - Improvement
PROMIS	Patient-Reported Outcomes Measurement Information System
SAE	serious adverse event
SAP	statistical analysis plan
SD	Standard Deviation
SE	Standard Error
SOC	system organ class
TEAE	treatment-emergent adverse event

1. INTRODUCTION

This statistical analysis plan (SAP) provides a technical and detailed elaboration of the statistical analyses of efficacy and safety data as described in Protocol Amendment 3, dated 31 January 2020. Specifications for tables, figures, and listings are contained in a separate document. Actigraphy and Ecological Momentary Analysis (EMA) data collected on the Handheld Device will be analyzed as described in a separate, stand-alone SAP.

2. OBJECTIVES

2.1 Primary Objective

The primary objective of this study is to assess the safety and tolerability of pimavanserin and low-dose quetiapine compared to placebo in subjects with Parkinson's disease.

2.2 Exploratory Objective

The exploratory objectives of this study are:

- to explore the sensitivity of assessments/instruments that are novel for evaluating the experience of subjects with Parkinson's disease with respect to sedation/sleep, cognition, and other non-motor symptoms.
- to explore the effects of pimavanserin and low-dose quetiapine compared to placebo in subjects with Parkinson's disease on:
 - Daytime sleepiness
 - Nighttime sleep
 - Cognition
 - Other non-motor symptoms
 - Treatment satisfaction
 - Safety and tolerability

3. STUDY DESIGN

3.1 General Study Design

This study is a multicenter, randomized, double-blind, placebo and active-control, parallel-group pilot study in subjects with Parkinson's disease. The study will have 3 periods:

[figure not shown]
- Screening period (7-28 days)
- Double-blind treatment period (4 weeks)
- Safety follow-up period (30 [± 4] days)

The study completion date is defined as the date the final subject, across all sites, completes their final protocol-defined assessment (this includes the safety follow-up phone call). If the study is terminated for any reason, subjects remaining in the study will return to standard of care.

Up to 60 subjects will be randomized in a 1:1:1 ratio to pimavanserin, quetiapine, or placebo. Subjects for whom the Investigator does not increase the dose of blinded study drug consistent with 50 mg quetiapine at Week 1 (Visit 3) will be withdrawn from the study and replaced. A maximum of 12 subjects across treatment groups (20%) will be replaced for this and only this reason.

The study design is summarized in [Figure 1](#).

Figure 1 Schematic of Study Design

[figure not shown]

R= randomization

* Pre-drug actigraphy data and handheld device assessments are conducted prior to randomization (Baseline)

Note: A schematic for study drug dispensing and dose adjustments is provided in [Figure 2](#).

Figure 2 Schematic for Study Drug Dispensing and Dose Adjustments

* Week 2 (Visit 4) & Week 3 (Visit 5): Subjects may remain on blinded study drug dose consistent with 50 mg quetiapine or be optionally increased to 100 mg quetiapine.

Abbreviations: EOT=end of treatment; R=randomization

Note: Dose adjustments and study drug dispensing are only allowed at scheduled visits (i.e., not at unscheduled visits). Subjects should not take study drug on the mornings of clinic visit days until instructed to do so by the site staff. At Baseline and at each subsequent clinic visit, subjects will be dosed and will remain in the clinic for observation for a minimum of 60 minutes after dosing. At Week 1 (Visit 3), Week 2 (Visit 4), and Week 3 (Visit 5), the Investigator will be encouraged to increase the dose of blinded study drug, consistent with 50-100 mg quetiapine, based on the Investigator's assessment of clinical response. Dose adjustments will be implemented through the IRT. In actuality, only the dose of quetiapine would be increased (to 50 mg at Week 1 [Visit 3] and then optionally to 100 mg at Week 2 [Visit 4] or Week 3 [Visit 5]); the pimavanserin dose will remain fixed at 34 mg per day throughout the study. Subjects for whom the Investigator does not increase the dose of blinded study drug consistent with 50 mg quetiapine at Week 1 (Visit 3) will be withdrawn from the study and replaced. The Investigator will be blinded to study drug and thus will not know whether their decision to increase the dose of blinded study drug results in an actual increase in study drug dose. The dose of study drug (pimavanserin, quetiapine or placebo) may not be decreased. If a subject cannot tolerate their dose, they must be withdrawn from the study.

3.2 Schedule of Assessments

The schedule of events and assessments, the schedule of assessments for subjects on the handheld device, and the schedule of assessments for informants on the handheld device are presented in [Tables 6, 7](#) and [8](#) in the appendix.

3.3 Randomization

Eligible subjects will be randomized into one of three treatment groups (pimavanserin, quetiapine, or matching placebo) in a 1:1:1 ratio using an Interactive Response Technology (IRT) system. The assignments will be based on a pre-generated permuted-block randomization schedule.

3.4 Blinding

This is a double-blind study. Blinding is assured by restricting access of Investigators and Sponsor personnel and/or designee to the treatment codes, and providing identical encapsulated tablets and packaging for the pimavanserin, quetiapine, and placebo treatments.

Unblinding of individual treatment assignment during the study is discouraged. The Investigator may break the blind in the event of a medical emergency if it is considered necessary for the care of the subject. The Investigator should attempt whenever possible to contact the Medical Monitor before unblinding a subject's treatment to discuss the event.

For the final analysis, the treatment codes for all subjects will be released to ACADIA after all subjects have completed the study and the clinical database (Medidata RAVE) is locked.

3.5 Determination of Sample Size

This is a pilot study and is not powered for statistical significance. Up to 60 subjects will be randomized into the study.

3.6 Coronavirus Disease 2019

In March, 2020, the emerging coronavirus disease 2019 (COVID-19) pandemic resulted in implementation of urgent safety measures designed to ensure subject safety. Mechanisms to record information on the potential impact of the COVID-19 pandemic on data itself, as well as data collection and integrity, were implemented (as detailed in the “Guidance for Site Documentation and Data Management Querying of Data Impacted by COVID-19” [GSD] in the Data Management Plan, Appendix B).

Due to COVID-19, Screening and enrollment into this study were temporarily halted in March 2020, and the decision was made to permanently stop the study as of 24 September 2020. The impact of COVID-19 on the statistical analysis is discussed in each of the relevant sections of this SAP.

4. ANALYSIS SETS

The Randomized Analysis Set will consist of all subjects who were randomized. Subjects will be classified according to the randomized treatment assignment.

The Safety Analysis Set will consist of all subjects who have taken at least 1 dose of study drug. Subjects will be classified according to the actual treatment received. Safety analyses will be based on the Safety Analysis Set.

The Exploratory Analysis Set will consist of randomized subjects in the Safety Analysis Set excluding subjects who were replaced due to no increase of the dose of blinded study drug consistent with 50 mg quetiapine at Week 1 (Visit 3). Subjects will be classified according to the randomized treatment assignment. Exploratory efficacy analyses will be based on the Exploratory Analysis Set.

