3.1.2 Double-blind Treatment Period (4 Weeks)

The Baseline visit (Visit 2) may occur after screening procedures are completed, subject eligibility has been confirmed, and no earlier than 7 days after the subject has been given the wearable device. At the Baseline visit (Visit 2), eligible subjects will be randomized in a 1:1:1 ratio to pimavanserin 34 mg, quetiapine 25 mg, or matching placebo.

Subjects who are randomized to the quetiapine treatment group will begin dosing at 25 mg. At Week 1 (Visit 3), Week 2 (Visit 4) and Week 3 (Visit 5), the Investigator will be encouraged to increase the dose of blinded study drug, consistent with 50-100 mg quetiapine, based on the Investigator's assessment of clinical response ([Figure S-2](#)). Dose adjustments will be implemented through interactive response technology (IRT) system. In actuality, only the dose of quetiapine would be increased (to 50 mg at Week 1 and then optionally to 100 mg at Week 2 or Week 3); the pimavanserin dose will remain fixed at 34 mg per day throughout the study. The Investigator will be blinded to study drug and thus will not know whether their decision to increase the dose of blinded study drug results in an actual increase in study drug

dose. The dose of study drug (pimavanserin, quetiapine or placebo) may not be decreased. If a subject cannot tolerate their dose, they must be withdrawn from the study.

Subjects for whom the Investigator does not increase the dose of blinded study drug consistent with 50 mg quetiapine at Week 1 (Visit 3) will be withdrawn from the study and replaced. A maximum of 12 subjects across treatment groups (20%) will be replaced for this and only this reason.

Assessments in the clinic will be conducted at Weeks 0 (Baseline), 1, 2, 3, and 4/end of treatment (EOT). Assessments on the handheld device will be collected from Baseline to Week 4/EOT on a regular basis (see [Table S-2](#)).

Subjects will be provided standard of care treatment per investigator judgment for 3 months following their completion of the double-blind treatment period.

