9.4 Subject Populations for Analysis

The Safety Analysis Set will consist of all subjects who have taken at least 1 dose of study drug. Safety analyses will be based on the Safety Analysis Set.

The Exploratory Analysis Set will consist of randomized subjects in the Safety Analysis Set excluding subjects who were replaced due to no increase of the dose of blinded study drug consistent with 50 mg quetiapine at Week 1 (Visit 3). Exploratory analyses will be based on the Exploratory Analysis Set.

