5. DATA HANDLING CONVENTIONS

All data collected in the study will be listed, excluding actigraphy data or data collected on the Handheld Device.

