5.3.1 Unscheduled Assessments

Both Scheduled and Unscheduled assessments, including the assessments at early termination visits, will be used for planned timepoint analyses. All assessments will be presented in data listings.

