6. SUBJECT DISPOSITION

For subjects who participate in the screening phase but are not randomized (screen failures), their demographics information (including age, sex, and primary race), screen failure reasons (the specific inclusion/exclusion criterion, or criteria, not met or other reasons including the reason due to COVID-19) and protocol version will be listed. If a subject is re-screened, then the re-screening subject ID and the final enrollment status (whether eventually enrolled) will also be displayed in this listing. In addition, the frequency that the screen failure reasons are reported will also be summarized. Note that one subject may be deemed ineligible for multiple inclusion/exclusion criteria and may be allowed to rescreen with the permission of the Medical Monitor, provided the screen failure was due to a temporary condition that subsequently resolved.

The number of sites that screened at least 1 subject, number of sites that randomized at least 1 subject, number of subjects screened, and number of unique subjects screened will be tabulated. In addition, the number of subjects enrolled at each site will also be tabulated by analysis set and by treatment group and overall.

For randomized subjects, the number and percentage of subjects in the Safety Analysis Set and Exploratory Analysis Set will be summarized by treatment group and overall. A listing will be provided displaying all subjects excluded from the Safety or Exploratory Analysis Sets, and will include reason(s) for exclusion.

Within each analysis set, the number and percentage of subjects who completed the study or discontinued (all discontinued and by discontinuation reasons including the reason due to COVID-19) will also be summarized by treatment group and overall.

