12.1 Efficacy Variables

Exploratory Efficacy Endpoints Measured at Study Visits

- Change from Baseline to Week 4 in
 - Time to completion or maximum time of TMT Parts A and B,
 - HVLT-R recognition discrimination index, and
 - PD NMS total score
- CGI-I score at Week 4
- PGI-I score at Week 4

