13. METHODS OF EFFICACY ANALYSES

The change from Baseline in the exploratory efficacy endpoints measured at scheduled visits including time to completion or maximum time of TMT Parts A and B, HVLT-R recognition discrimination index, and PD NMS total score will be analyzed using an analysis of covariance model (ANCOVA) using observed scores. The model will include treatment group as a factor and the corresponding Baseline measure as a covariate.

Summary statistics (observed and change from Baseline), LS means, the between-group differences (Pimavanserin – Placebo and Quetiapine – Placebo) in LS means with the corresponding 95% confidence intervals, p-values, and the effect sizes (Cohen's d) will be presented at each post-Baseline visit for the Exploratory Analysis Set.

CGI-I score will be analyzed using a similar ANCOVA model with treatment group as a factor and Baseline CGI-S score as a covariate.

PGI-I score will be analyzed using an analysis of variance model with treatment group as a factor.

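### The Week 1 treatment comparison is made on a set that omits subjects whose blinded dose was not increased at Week 1; an all-dosed Week 1 analysis should be added

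*SAP*

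**What the plan says.** SAP Section 4 defines the Exploratory Analysis Set as randomised subjects who took study drug, "excluding subjects who were replaced due to no increase of the dose of blinded study drug consistent with 50 mg quetiapine at Week 1". Those who remain are classified as randomised. Protocol Section 9.4 has the same exclusion and adds: "Exploratory analyses will be based on the Exploratory Analysis Set".

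Protocol Section 3.1.2 places the dose decision at Visit 3, after randomisation and about a week of treatment, and bases it on the investigator's "assessment of clinical response". A subject not increased is withdrawn and replaced, up to 12 subjects.

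SAP Section 13 states that least-squares mean differences from placebo, 95% confidence intervals, p-values and Cohen's d "will be presented at each post-Baseline visit for the Exploratory Analysis Set". Week 1 is one of those visits. The schedule of events places the Trail Making Test (TMT), HVLT-R, CGI-I and PGI-I at Week 1. SAP Table 1 sets the Week 1 window at Days 2–11, and SAP Section 5.3.1 adds: "Both Scheduled and Unscheduled assessments, including the assessments at early termination visits, will be used for planned timepoint analyses".

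For excluded subjects, SAP Section 5 provides "All data collected in the study will be listed, excluding actigraphy data or data collected on the Handheld Device". SAP Section 6 provides "A listing will be provided displaying all subjects excluded from the Safety or Exploratory Analysis Sets", with reasons, and counts membership of each set by arm. No analysis of their Week 1 values is planned.

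**The concern.** Randomisation protects a comparison only while the arms keep the subjects they were given. Here, whether a subject counts at Week 1 depends on something judged after treatment began and tied to response. The treatments may already differ by then, so the excluded fraction, and the kind of subject excluded, may differ by arm. Blinding means that one rule is applied in all arms. It does not stop treatment from influencing the decision through response.

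The loss is avoidable at Week 1 because the values may exist: the tests are scheduled at the visit where the decision is made, and early-termination data are usable. The rule is also uneven. A subject withdrawn at about the same time for intolerance is not covered by the exclusion and keeps the Week 1 value in the analysis.

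There is a smaller question of wording. Membership turns on having been replaced. Enrolment was halted in March 2020 and the study stopped with 11 randomised (SAP Sections 3.6 and 19), so a subject could be withdrawn for no increase without any later enrolment to replace them. The SAP, dated 19 October 2020, postdates the stop and gives no rule for that case.

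At stake are the Week 1 exploratory estimates in a pilot meant to guide later designs.

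**Working it through.** **The plan's own figure.** The replacement cap is 20% of 60: 0.20 × 60 = 12, as stated. It cannot bind with 11 randomised. There is no power calculation to reproduce.

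**Inputs.** From the documents: 11 randomised, three arms at 1:1:1; ANCOVA with treatment and one baseline covariate, or ANOVA without a covariate for PGI-I; two-sided 5%. Assumed: a 4/4/3 split, everyone with Week 1 data, no precision gain from baseline, the exclusion rates, and the link between the decision and the outcome. The documents give no expected rate of non-increase; 20% is the cap on replacement.

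**1. Could anyone be affected?** If each subject has probability p of not being increased, P(at least one of 11) = 1 − (1 − p)^11. For p = 5%, 10% and 20% this is 43%, 69% and 91%.

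**2. Bias with no true difference, when a correlated response drives the decision.** If a fraction p of an arm is removed by a threshold on a latent response that has correlation r with the outcome, the retained mean shifts by r·φ(z_p)/(1 − p).
- p = 20%: 0.350r. p = 10%: 0.195r. p = 5%: 0.109r.
- 20% v 5%: 0.241r, which is 0.05 SD at r = 0.2, 0.12 at 0.5 and 0.19 at 0.8.
- 20% v 10%: 0.155r, which is 0.03 to 0.12 SD for r = 0.2 to 0.8.
- r = 0, or equal fractions removed in the same way: 0.

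The sign depends on which arm loses more and on whether good or poor responders are dropped. A simulation at 20% v 5% and r = 0.5 gave 0.120 SD with the exclusion and −0.001 SD with everyone kept. The theoretical extreme (20% of one arm, none of the other, r = 1) is 0.35 SD; it is a bound and not a plausible case.

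**3. Bias when the analysed outcome itself drives the decision.** Take the outcome as normal with SD 1 and P(not increased) = logistic(a + b·y). Set a so that the three-arm average is 5%, 10% or 20%, with true differences of 0 to 0.75 SD and b from 0 to 1.6. Numerical integration gives attenuation of 0 to 0.06, 0 to 0.10 and 0 to 0.15 SD. The worst case at 20% excludes 29.8% v 15.1%, and the difference falls from 0.75 to 0.596 SD.

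**4. Scale against the noise.** The SE of a difference is √(1/4 + 1/4) = 0.707 SD, or √(1/4 + 1/3) = 0.764 SD. The largest figure in step 2 for r up to 0.8 is 0.193/0.707 = 27% of one SE.

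**5. Precision.** One exclusion removes 1/4 or 1/3 of an arm. In comparisons that involve that arm, the 95% half-widths in SD are:

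| Comparison before → after | ANCOVA (df 7 → 6; t 2.365 → 2.447) | PGI-I ANOVA (df 8 → 7; t 2.306 → 2.365) |
|---|---|---|
| 4 v 4 → 4 v 3 (SE 0.707 → 0.764) | 1.67 → 1.87 | 1.63 → 1.81 |
| 4 v 3 → 3 v 3 (SE 0.764 → 0.816) | 1.81 → 2.00 | 1.76 → 1.93 |
| 4 v 3 → 4 v 2 (SE 0.764 → 0.866) | 1.81 → 2.12 | 1.76 → 2.05 |

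If the excluded value lies 1 SD from the mean of the rest of its arm, the unadjusted arm mean moves by 1/4 = 0.25 or 1/3 = 0.33 SD.

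**6. Week 4.** SAP Section 12.3 imputes nothing. A subject withdrawn at Visit 3 whose early-termination visit falls before Day 26 contributes nothing to the Week 4 window in either set, so the observed-case Week 4 result is the same.

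**The case against.** The strongest case against concerns weight. The named endpoints are at Week 4, for example "CGI-I score at Week 4" in SAP Section 12.1; Protocol Section 9.5.2.1 bases treatment comparisons on Week 4; and Protocol Section 9.2 disclaims definitive comparisons. Before Visit 3 the quetiapine arm receives only its starting dose, so Week 1 says little about the regimen of interest. The exclusion is prespecified, made under blind, and disclosed by listings and by counts per arm. All of this stands, and it keeps the point minor. None of it restores the as-randomised comparison that SAP Section 13 sets out to report at Week 1.

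The excluded subjects' values are also not assured. Protocol Section 4.4.1 asks only for reasonable effort at early termination. The clinician-administered tests are done at least an hour after dosing, and the order of decision, dosing and testing at Visit 3 is not fixed. A withdrawn subject may be tested under different conditions or not at all. This stands too, so the fix is limited to values actually observed.

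The bias sizes are hypothetical. Fractions such as 20% v 5% cannot occur in arms of three or four, so steps 2 and 3 describe expected bias under a rule and not an effect in this dataset.

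A reader might infer that the word replaced makes the set inconsistent, with like subjects classified differently. The documents do not go that far. Protocol Section 3.1.2 and SAP Section 3.1 treat withdrawal and replacement as one consequence, so the word may simply mean not increased. It is a wording query that should be closed.

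**Conclusion.** The point holds as a minor one. The Week 1 comparison is presented as randomised on a set selected after randomisation, and no all-dosed estimate is planned beside it. The illustrative bias is 0 to 0.19 SD in either direction, at most about 27% of one SE, for assumed exclusion fractions up to 20% v 5% and correlations up to 0.8. The more tangible cost is precision: one exclusion widens the ANCOVA half-width from 1.67–1.81 to 1.87–2.12 SD under the assumed 4/4/3 split. If nobody was left un-increased, the effect is nil, and the documents do not say.

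A reader might conclude that the study's main findings are biased, or that the protocol-defined set should be abandoned. Neither follows. The Week 4 observed-case results are the same in both sets, and the primary analysis of treatment-emergent adverse events uses the Safety Analysis Set, which keeps these subjects. No figure is claimed for the handheld or actigraphy data, whose analysis lies in a separate SAP.

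**What to change.** 1. In SAP Section 13, add a Week 1 analysis of TMT, HVLT-R, CGI-I and PGI-I in all randomised subjects who took at least one dose, as randomised, using every observed Week 1 or early-termination value in the window. Show it beside the result on the protocol-defined set, and base any Week 1 treatment comparison on it. The protocol-defined set stays as it is for Week 4.
2. In SAP Section 4, define the exclusion by the recorded decision not to increase at Week 1 and not by replacement.
3. Record both changes in SAP Section 19, and check that the separate handheld and actigraphy SAP does the same.

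The cost is some wording, one Section 19 entry and one extra table run. The downsides are that the added Week 1 summary includes subjects who did not go on to the increased dose, so it describes assigned treatment, and that the SAP adds to the protocol's plan after the study stopped. Counts per arm and reasons for exclusion are already planned in SAP Section 6. No position is taken on the withdrawal rule.
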